#### *8.2.1.4 Suspected Unexpected Serious Adverse Reaction*

A SUSAR is any suspected adverse reaction related to the study vaccine that is both unexpected and serious.

#### *8.2.2 Study Reporting Period for Adverse Events*

The reporting period for all adverse events begins on the date the informed consent is signed. Solicited adverse events are recorded in the eDiary up to 7 days post-vaccination. All other events are recorded in the eCRF at all clinic visits throughout the study. All SAEs and/or AESIs are recorded until the final study visit and for all serious or study vaccine-related adverse events until these are resolved or until participant contact discontinues. Severe adverse events or SAEs that continue at the end of the study will be attempted to be followed until resolved or stabilised.

Adverse event information will be collected at study visits and participant will be instructed to call study team members to report any abnormalities during the intervals between study visits and to come to the study centre if medical evaluation is needed and the urgency of the situation permits.

#### *8.2.3 Reporting Exemptions*

No reporting exemptions have been identified for this study.

#### *8.2.4 Recording and Assessment of Adverse Events by the Investigator*

Solicited adverse events are recorded in the eDiary up to 7 days post-vaccination. All other adverse events are recorded in the eCRF at all clinic visits throughout the study. All adverse events, both those observed by study team members and those spontaneously reported by the participant, will be recorded in the eCRF. Solicited adverse events will be reported using pre-defined terms. Unsolicited adverse events will be reported using a recognised medical term or diagnosis that accurately reflects the event.

Adverse events will be assessed by the Investigator, or a medically qualified study team member, for severity, relationship to study vaccine, action taken, outcome and whether the event meets criteria as an SAE according to the following guidelines:

#### 8.2.4.1 Assessment of Severity

Whenever possible, the severity of adverse events will be graded according to the toxicity table in [Appendix 1](#). The scale shown in [Table 3](#) will be used to assess severity of adverse events not listed in [Appendix 1](#).

**Table 3 Severity Grading of Adverse Events not listed in the Toxicity Table for Clinical and Laboratory Abnormalities**

Grade	Severity	
1	Mild	Asymptomatic or mild symptoms; clinical or diagnostic observations only; or intervention not indicated; no disruption of normal daily activity.
2	Moderate	Minimal, local, or non-invasive intervention indicated; discomfort sufficient to reduce or affect daily activity.
3	Severe	Severe or medically significant, but not immediately life-threatening; hospitalisation or prolongation of hospitalisation indicated; inability to work or perform normal daily activity.
4	Life-threatening	Represents an immediate threat to life.
5	Fatal	Death as a result of this adverse event

A change in severity of an adverse event will not be recorded as a new adverse event. Only the highest severity level that occurs during the entire period of the adverse event will be recorded on the eCRF with the onset and resolution dates encompassing the entire duration of the event.

Note: It is important to distinguish between serious and severe adverse events. Severity is a measure of intensity whereas seriousness is defined by the criteria in [Section 8.2.1.3](#).

#### 8.2.4.2 Assessment of Relationship

Solicited adverse events of vaccination site reactions will be considered causally related to study treatment.

For all other adverse events, the Investigator will determine a **causal relationship** to the study vaccine. A number of factors will be considered in making this assessment, including: 1) the temporal relationship of the event to the administration of the study vaccine 2) whether an alternative aetiology has been identified and 3) biological plausibility.

Causality of all adverse events should be assessed by the Investigator using the following question:

***“Is there a reasonable possibility that the adverse event may have been caused by the study vaccine?”***

- **YES (related):** There is a reasonable possibility that the study vaccine contributed to the adverse event
- **NO (not related):** There is no reasonable possibility that the adverse event is causally related to the administration of the study vaccine. There are other, more likely causes and administration of the study vaccine is not suspected to have contributed to the adverse event

The Investigator is required to provide an assessment of relationship of AEs to the vaccine or study procedures and determines causality. The Sponsor and local medical monitor can add another causality assessment to the Investigator’s causality. However, the causality given by the Investigator must not be downgraded by the Sponsor or the local medical monitor. If the

Sponsor or the local medical monitor disagrees with the Investigator's causality assessment, the opinion of both the Investigator, the Sponsor and the local medical monitor should be provided with the report.

Every effort should be made by the Investigator to determine the existence of any pre-existing conditions (e.g. headache in adults or rashes in infants on study Day 0 with onset prior to study vaccination) that must be taken into consideration when assessing causal relationship of an adverse event. Pre-existing conditions should be recorded in the eCRF as baseline history and substantiated by appropriate source documentation. Intermittent conditions such as headaches may not be present on study Day 0 but may represent an adverse event if the intensity or duration of the event is worse than usual following study vaccine.

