#### *8.2.5.3 Medical Review and Reporting by the Sponsor*

The Sponsor (or designee) will determine expedited reporting requirements for each reported SAE according to local requirements based upon:

- Investigator's assessment of causality and seriousness
- Expectedness

The expectedness of an SAE is assessed by the Sponsor in the overall classification of SAEs for expedited reportability. The current Investigator's Brochure section "Reference Safety

Information” will be used as the reference for determination of expectedness and risk assessment of vaccine-related adverse events and Section 4.8 of the Nivolumab SmPC will be used to assess the expectedness for nivolumab related events.

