### **8.2.7 Post-Study Adverse Events**

At the final study visit, the Investigator should instruct each participant to report to the Investigator any subsequent adverse events that the participant's personal physician believes could be related to study vaccine or study procedures.

The Investigator should notify the Sponsor (or designee) of any death, SAE or other adverse event of concern occurring at any time after a participant has discontinued study vaccine if the event is believed to be related to study vaccine or study procedures. The Sponsor (or designee) should also be notified if the Investigator becomes aware of the development of cancer or a congenital anomaly/birth defect in a subsequently conceived offspring of a participant that participated in this study.

The Investigator should record the event in the eCRF; if the eCRF is no longer available, the Investigator should report the event directly to the Sponsor (or designee).

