10.5.2 AE Causality

For unsolicited AEs, the Investigator will determine a causal relationship to the study vaccines and nivolumab.

Missing information regarding relationship to study vaccines or nivolumab, related/not related, will be handled using the worst-case approach. That is, unsolicited AEs with missing relationship to either study vaccines or nivolumab will be considered as "related".

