12.7.2 Other Safety Endpoints

12.7.2.1 Other Adverse Events

An overall summary of treatment-emergent adverse events, including the number of events reported, will be provided for:

- Any AEs
- Any AEs within 28 days of first vaccination
- Any AEs within 28 days of second vaccination
- Any grade 3 or greater AEs within 28 days of first vaccination
- Any grade 3 or greater AEs within 28 days of second vaccination
- Any AEs related to study vaccines
- Any AEs related to nivolumab

- Any AEs related to study vaccines or nivolumab
- Any grade 3 or greater AEs related to study vaccines
- Any grade 3 or greater AEs related to nivolumab
- Any grade 3 or greater AEs related to study vaccines or nivolumab
- Any AEs with outcome of death
- Any serious AEs
- Any serious AEs related to study vaccines
- Any serious AEs related to nivolumab
- Any serious AEs related to study vaccines or nivolumab
- Any AEs leading to discontinuation of study vaccines
- Any AEs leading to discontinuation of nivolumab
- Any AEs leading to discontinuation of study vaccines or nivolumab
- Any AEs of special interest

Deaths will be identified using the AE eCRF.

In addition, individual summary tables by SOC and PT will be provided for each category (with the exception of any AEs with outcome of death) in the overall TEAE table and presented similarly to the primary endpoint in Section 12.7.1.1. A by-participant summary of all TEAEs leading to death, serious TEAEs, and TEAEs leading to discontinuation of study vaccines or nivolumab will be produced.

AEs leading to discontinuation of study vaccines or nivolumab are defined as any AE with Action Taken with Study Vaccines = 'Drug Withdrawn' or Action Taken with Nivolumab = 'Permanently Discontinue' recorded on the Unsolicited AEs eCRF.

TEAEs will be further summarised by maximum severity (grade 1, grade 2, grade 3, grade 4, grade 5) within each SOC and PT. Participants with multiple events within a particular SOC or PT will be counted under the category of their most severe event within that SOC or PT.

Non-treatment-emergent AEs will be presented by SOC and PT.

All adverse events (including non-treatment-emergent events) recorded on the eCRF will be listed separately.

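### The protocol judges causality, adverse reactions and SUSARs against the study vaccine only, while its own expectedness rule and the SAP need a separate nivolumab relationship

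*Protocol*

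**What the plan says.** Protocol 5.1 describes the two study vaccines (5.1.1) and nivolumab (5.1.2) as separate products, and 5.2.1 speaks of vaccine doses given with or without nivolumab.

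Protocol 8.2.4.2 then states: "Causality of all adverse events should be assessed by the Investigator using the following question". The question is "Is there a reasonable possibility that the adverse event may have been caused by the study vaccine". The negative answer is defined in the same terms: "There is no reasonable possibility that the adverse event is causally related to the administration of the study vaccine". The paragraph that follows requires the investigator to assess relationship to the vaccine or to study procedures. Nivolumab is not named.

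Section 8.2.1.2 defines an adverse reaction as a response to study vaccine. Section 8.2.1.4 says: "A SUSAR is any suspected adverse reaction related to the study vaccine that is both unexpected and serious". Section 8.2.7, on events after the study, asks for notification "if the event is believed to be related to study vaccine or study procedures".

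Two places take a different view. Protocol 8.2.5.3 says that "Section 4.8 of the Nivolumab SmPC will be used to assess the expectedness for nivolumab related events". SAP 10.5.2 says that, for unsolicited events, "the Investigator will determine a causal relationship to the study vaccines and nivolumab". SAP 12.7.2.1 builds on this with rows such as "Any grade 3 or greater AEs related to nivolumab", and SAP 16.0 lists Table 14.3.2.14, nivolumab-related events of Grade 3 or greater, as both a DMC and an interim output.

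**The concern.** Groups 3 and 4 add a checkpoint inhibitor with its own immune-related toxicity, and the safety of that combination is part of the primary objective. A reader of the tables will want to know whether an event was judged to be due to the vaccine, to nivolumab or to both. The protocol's question does not separate these. An investigator who believes nivolumab alone was responsible and follows the text has only one answer, that the event is not related. The SUSAR definition then excludes the event as well.

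Two things are at stake. The first is correct classification of serious events, since 8.2.5.3 bases expedited reporting on the investigator's causality and seriousness assessment together with expectedness. The DMC's 24-hour notices, for vaccine-related SAEs (8.1.5) and for SUSARs (8.2.5), inherit the same classification. The second is the basis of the SAP's nivolumab-related tables, which summarise an assessment that the protocol neither requires nor defines.

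**Working it through.** No power, error rate or effect size enters this point, so the plan has no figure to reproduce. The check is a comparison of texts, followed by three short counts.

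**Step 1. Which product does each provision name?**

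| Provision | Product named |
|---|---|
| Protocol 8.2.1.2, adverse reaction | Study vaccine |
| Protocol 8.2.1.4, SUSAR | Study vaccine |
| Protocol 8.2.4.2, causality question and both answers | Study vaccine |
| Protocol 8.2.4.2, required assessment | Vaccine or study procedures |
| Protocol 8.2.5, SAE assessment | Study vaccine or an alternative aetiology |
| Protocol 8.2.7, after the study | Study vaccine or study procedures |
| Protocol 8.2.5.3, expectedness | Vaccine and nivolumab, each with its own reference |
| SAP 10.5.2, causality | Study vaccines and nivolumab |

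**Step 2. Follow one event through the protocol.** Take a serious event that the investigator attributes to nivolumab and not at all to the vaccine.
- 8.2.4.2: no reasonable possibility of a vaccine cause, and another cause is more likely, so the answer is not related.
- 8.2.1.2 and 8.2.1.4: not a response to study vaccine, so neither an adverse reaction nor a SUSAR.
- 8.2.5.3: expectedness is to be judged against the nivolumab SmPC if the event is nivolumab-related, but no earlier step assigns that label.

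The sequence contradicts itself at the last step. The amendment history is consistent with this. Version 4.0 added the SmPC sentence to 8.2.5.3, and its listed changes do not include the causality question or the SUSAR definition.

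**Step 3. SAP rows that use nivolumab causality.** SAP 12.7.2.1 lists 20 rows. Those needing the nivolumab relationship are all events, Grade 3 or greater events, and serious events, each shown for nivolumab and for study vaccines or nivolumab: 3 × 2 = 6 of 20. Each row also has its own table by system organ class and preferred term. SAP 6.1, which lists departures from the protocol, does not mention the added assessment.

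**Step 4. Participants in the nivolumab groups.** Group 3 is planned at 16 and Group 4 closed at 9 (SAP 8.1): 16 + 9 = 25. With Group 1 at 10 and Group 2 planned at 16, the total is 10 + 16 + 16 + 9 = 51.

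**Step 5. Follow-up after nivolumab.** The last planned nivolumab dose is at Day 28 and Month 9 is Day 273 (SAP Table 3): 273 − 28 = 245 days. At 30.4 days per month (SAP 10.3) that is 245 / 30.4 ≈ 8.1 months of adverse event collection.

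**The case against.** The strongest reply is that the safety system works despite the wording, and much of it stands.

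- **SAE reporting.** Section 8.2.5 sends all SAEs in the study period to the Sponsor regardless of relationship. Section 8.3 sends AESIs, largely the nivolumab-type immune events, by the same route. The Sponsor and the local medical monitor may add their own causality view (8.2.4.2), and 8.2.5.4 also covers other significant safety issues. A reader might infer that serious nivolumab reactions escape expedited reporting. The documents do not support that. They show a wrong label at the investigator's step, which the Sponsor can correct.
- **Events after the study.** A reader might infer that a late nivolumab event need not be reported at all. That is also too strong. Collection runs about eight months past the last nivolumab dose, and serious events are followed until they resolve or stabilise. What remains is that 8.2.7 states no explicit duty for nivolumab-related events, although Appendix 2 says immune-related events can appear months after treatment.
- **Primary endpoint.** The nivolumab safety endpoint counts events, SAEs and Grade 3 or greater events without a relatedness condition, so it is unaffected.
- **Data.** The SAP says the nivolumab judgement is made and cites an eCRF field for action taken with nivolumab, so the relationship field probably exists. The eCRF is not among the documents, and missing data are not shown.
- **Loose terms.** Protocol Table 1 places nivolumab under a study vaccine heading, and 8.2.1.2 judges unexpectedness against prescribing information as well as the Investigator's Brochure. Because nivolumab always follows a vaccine dose on the same day, and a positive answer needs only a possible vaccine contribution, many investigators would answer yes.

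These points limit the consequence. They do not remove the contradiction: the operative text in 5.1 and 5.2.1 separates the products, and an event attributed to nivolumab alone still has no correct answer under 8.2.4.2.

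**Conclusion.** The concern holds as a fault of classification and of protocol–SAP consistency. Followed literally, the protocol labels an event caused by nivolumab alone as not related and excludes it from the SUSAR definition. Its own expectedness rule and the SAP both assume that a nivolumab relationship has been assigned. The affected output is 6 of 20 rows in the overall summary, the tables built from those rows, and Table 14.3.2.14. The affected population is about 25 of 51 participants, taking Group 3 at its planned 16.

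Two assumptions carry this: that study vaccine excludes nivolumab, as 5.1 and 5.2.1 indicate, and that investigators apply 8.2.4.2 as written. If the eCRF has a nivolumab relationship field, the tables can be filled, but from an assessment the protocol does not define. If it has none, SAP 10.5.2 counts missing relationship as related, so the nivolumab rows would be inflated rather than empty. As worded, that rule makes no exception for Groups 1 and 2, who receive no nivolumab.

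The point is worth correcting. It does not call the primary nivolumab safety endpoint into question.

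**What to change.** - In protocol 8.2.4.2, ask the causality question twice, once for the study vaccine and once for nivolumab, with yes and no answers defined for each.
- In 8.2.1.2 and 8.2.1.4, define an adverse reaction and a SUSAR as related to any investigational product (study vaccine or nivolumab).
- Bring 8.2.5 and 8.2.7 into line with 8.2.5.3 and SAP 10.5.2, so that SAE assessment and post-study notification name nivolumab.
- If the protocol is not amended, list the separate nivolumab assessment in SAP 6.1 as a difference from the protocol, and confirm that the eCRF collects it.

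The cost is protocol wording and possibly a few more reportable events. The SAP already assumes both relationship fields, so its planned tables need no change.

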#### *8.2.4.3 Action Taken with Study Vaccine*

The action taken with the study vaccine will be recorded as None, as only one dose is given.

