### ***3.1.4 Individual Stopping Rules (All Vaccinated Study Participants)***

In addition to the above stated group holding rules, stopping rules for individual participants will apply (i.e. in addition to withdrawal of individuals from a second vaccination). Study participants who present with at least one of the following stopping rules will be withdrawn from further vaccination in the study:

- **Local reactions:** injection site ulceration, abscess or necrosis
- **Laboratory AEs:**
  - The participant develops a Grade 3 laboratory adverse event considered possibly, probably or definitely related within 7 days after vaccination and persisting continuously at Grade 3 for >72 hours
- **Systemic solicited adverse events:**
  - The participant develops a Grade 3 systemic solicited adverse event considered possibly, probably or definitely related within 2 days after vaccination (day of vaccination and one subsequent day) and persisting continuously at Grade 3 for >72 hours
- **Unsolicited adverse events:**
  - The participant has any Grade 3 adverse event considered possibly, probably or definitely related to vaccination, persisting continuously at Grade 3 for >72 hours
  - The participant has an SAE considered possibly, probably or definitely related to vaccination
  - The participant has an acute allergic reaction or anaphylactic shock following the administration of vaccine investigational product

If the participant has an acute illness (moderate or severe illness with or without fever) or a fever (oral temperature > 37.5°C) at the scheduled time of administration of investigational product, the participant will not receive the vaccine at that time. The vaccine may be administered to that participant at a later date within the time window specified in the protocol or the participant may be withdrawn from the study at the discretion of the Investigator.

All vaccinated participants will be followed for safety until resolution or stabilisation (if determined to be chronic sequelae) of their SAEs.

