### 5.2.1 Study Vaccines

All participants will receive two doses of study vaccine, with or without nivolumab, on Day 0 and Day 28. Both vaccinations will be given by intramuscular injection into the deltoid muscle, to the same, non-dominant arm in a participant, where possible. If a participant has a 0.5 log or greater drop in hepatitis B surface antigen at Day 35, they may receive a booster dose of MVA-HBV at Month 3, at the Investigator's discretion and after discussion with the Sponsor (UK participants only).

The ChAdOx1-HBV dose is 2.5 x 10^10 vp, based on the review of the two doses studied in study HBV001. This dose, or higher, of ChAdOx1-based vaccines has been safely used in hundreds of participants (see Investigator's Brochure), and thousands of people have been immunised with a ChAdOx1 COVID-19 vaccine at a dose of 5 x 10^10 vp.

The dose of MVA-HBV will be fixed at 1 x 10^8 pfu, as taken from historical data of previous studies. A 1.5 x 10^8 pfu MVA dose was used in nearly 2,000 healthy participants in influenza studies conducted by Oxford University and Vaccitech.

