## **8.2 Adverse Events**

### ***8.2.1 Definitions***

#### ***8.2.1.1 Adverse Event***

An adverse event is:

- Any untoward medical occurrence in a participant or clinical investigation subject administered a pharmaceutical product and which does not necessarily have to have a causal relationship with this treatment

- An adverse event can therefore be any unfavourable and unintended sign (including an abnormal laboratory finding), symptom or disease temporally associated with the use of study vaccine, whether or not considered related to the investigational product

An adverse event includes but is not limited to:

- Any clinically significant worsening of a pre-existing condition
- An adverse event occurring from overdose (i.e. a dosage higher than that prescribed by a healthcare professional for clinical reasons, or a dosage higher than that described in the Investigator's Brochure or on the marketed product label) of an investigational or marketed product, whether accidental or intentional
- An adverse event occurring from abuse (e.g. use for non-clinical reasons) of an investigational or marketed product
- An event related to a medical procedure or associated with the discontinuation of the previous use of an investigational or marketed product required by protocol (protocol related adverse event)
- Not all vital sign or laboratory abnormalities will be considered an adverse event. Usually these will be considered as an adverse event:
  - If Grade 3 (severe) or greater in severity
  - If judged to be clinically significant by the Investigator
  - If accompanied by clinical symptoms
  - If meeting the definition of a SAE
  - If resulting in dose modification, interruption or discontinuation of study vaccine
  - If requiring specific treatment

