#### *10.2.2.6.1 Adverse Events*

All adverse events will be listed, including the verbatim description and MedDRA preferred terms and system organ class (SOC).

TEAEs will be summarised by SOC and by preferred term. The incidence of TEAEs will be based on the numbers and percentages of participants with events and number of events. TEAEs will be further summarised by severity and relationship to study vaccine.

An overall summary of adverse event incidence will also be presented by study vaccine dose and overall to include the number and percentage of participants with at least one: TEAE, vaccine-related TEAE, Grade 3 to Grade 5 TEAE, death, SAE, vaccine-related SAE, AESI, vaccine-related AESI, TEAE leading to study vaccine discontinuation and TEAE leading to study discontinuation.

Narratives will be written for any deaths, other SAEs, AESIs, TEAEs leading to study vaccine discontinuation and TEAEs leading to study discontinuation.

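### Protocol 8.2.4.3 fixes action taken with study vaccine at None on a single-dose premise; this conflicts with the two-dose schedule and, if followed, empties the SAP's count of AEs leading to vaccine discontinuation

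*Protocol*

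**What the plan says.** Protocol 8.2.4.3 gives a recording rule and its reason: "The action taken with the study vaccine will be recorded as None, as only one dose is given". This is operative Version 6.0 text, not an entry in an amendment log.

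Other sections of the same protocol read differently:

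- 5.2.1: "All participants will receive two doses of study vaccine, with or without nivolumab, on Day 0 and Day 28".
- 3.1.4: "Study participants who present with at least one of the following stopping rules will be withdrawn from further vaccination in the study".
- 8.2.1.1, among the features that usually make a laboratory or vital sign abnormality an adverse event: "If resulting in dose modification, interruption or discontinuation of study vaccine".

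Protocol 10.2.2.6.1 requires the number and percentage of participants with at least one "TEAE leading to study vaccine discontinuation", and lists such events among those that receive a narrative.

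SAP 12.7.2.1 supplies the derivation. An AE leads to discontinuation of study vaccines or nivolumab if the vaccine action-taken field is *Drug Withdrawn* or the separate nivolumab field is *Permanently Discontinue*, as recorded on the Unsolicited AEs eCRF. No other criterion is given for the vaccine part.

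**The concern.** The reason stated in 8.2.4.3 does not agree with the schedule. With a second vaccination planned at Day 28, an event after Day 0 can lead to dose 2 being withheld, and 3.1.4 provides for exactly that. A site that follows 8.2.4.3 literally cannot record this outcome against the event.

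The field is not incidental, because the SAP builds a protocol-required safety count on it alone. A zero in that count could then mean either that no AE stopped vaccination or that the form was completed as the protocol instructs, and the table would not show which. Mixed practice between sites would make the count unreliable in a less visible way.

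The events for which the link matters most are non-serious related Grade 3 events of the kind listed in 3.1.4. An event that is not an SAE or AESI and does not end study participation has no narrative trigger in 10.2.2.6.1 other than vaccine discontinuation.

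**Working it through.** The plan states no figure to reproduce. The check applies the 8.2.4.3 rule to the SAP derivation and asks which counts can still be non-zero.

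**1. Derivation.** For each treatment-emergent AE, let V mean that the vaccine action-taken field is *Drug Withdrawn* and N that the nivolumab field is *Permanently Discontinue*. The SAP gives one joint definition, V or N. I read the vaccine-only row as V and the nivolumab-only row as N.

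**2. Apply 8.2.4.3.** If the vaccine field is always *None*, V is false for every AE. Then:

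- vaccine-only row = 0 in every group, whatever happened between Day 0 and Day 28;
- nivolumab-only row = N, unchanged, because 8.2.4.3 does not govern that field;
- combined row = (false or N) = N, identical to the nivolumab row.

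**3. Count the outputs.** The overall summary in SAP 12.7.2.1 has 20 rows, 3 of them on discontinuation (vaccines; nivolumab; vaccines or nivolumab). Two of these change, so 2 of 20 rows are affected. SOC/PT tables are planned for every category except AEs with outcome of death: 20 - 1 = 19 tables, of which the same 2 are affected. Table 14.3.2.25, marked for both DMC and interim use in SAP 16.0, lists participants on the combined definition and so loses every entry that rests on V alone.

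**4. Group 2 in the combined outputs.** Safety data are shown by regimen actually received (SAP 9.2.3, SAP Table 2). Of the 13 rows in SAP Table 2, 4 place a participant randomised to Group 3 or 4 in analysed Group 2:

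- Group 3 with no second vaccination;
- Group 3 given MVA-HBV without nivolumab;
- Group 4 with no nivolumab at either vaccination;
- Group 4 with no nivolumab at the first vaccination and no second vaccination.

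Five rows have no second vaccination, and 2 of those 5 move a participant into Group 2 from another group. Such participants had nivolumab assigned, so N can be true for someone analysed in Group 2. These are counts of table rows, not of participants.

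**5. What does not depend on the field.** The primary endpoints listed in Protocol section 2 and SAP 12.7.1 are AEs, SAEs, Grade 3 or greater AEs, AESIs, TEAEs, and laboratory and vital sign results. None uses action taken. Discontinuation counts sit under Other Safety Endpoints in SAP 12.7.2.

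**The case against.** The best defence is that the sentence may have had no effect. SAP 12.7.2.1 names *Drug Withdrawn* as a value on the Unsolicited AEs eCRF, and the SAP was revised after a dry run and after data had been received. That suggests that the form was not limited to *None*. If sites used the full set of values, 8.2.4.3 cost nothing. This stands as a limit on the consequence, but it does not remove the contradiction, and the documents do not include the eCRF instructions that would settle the matter.

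The information is also largely available elsewhere. AE term, severity and relatedness are tabulated. Disposition (SAP 12.1) and exposure (SAP 12.5) give reasons for stopping the regimen or missing a dose. The DMC and interim package includes Table 14.3.2.13, Table 14.3.2.27.a, the exposure table, and the end-of-treatment and TEAE listings. Protocol 8.4 requires events that preclude further vaccine to be reported within 24 hours. All of this stands. As described, however, none of it feeds the discontinuation count.

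Several stronger readings are tempting but not supported:

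- *That 8.2.4 also contradicts the sentence.* It has events assessed "for severity, relationship to study vaccine, action taken, outcome and whether the event meets criteria as an SAE", but according to the guidelines that follow, and 8.2.4.3 is one of them. Likewise 8.2.1.1 only presupposes that vaccine can be discontinued; it does not govern the field.
- *That the primary endpoints are compromised.* Step 5 of the working shows that they are not.
- *That the combined outputs must be empty in Groups 1 and 2, which are assigned no nivolumab.* For Group 2 as analysed this does not follow, by step 4.
- *That narratives would be missed.* The documents do not say which field selects them.
- *That solicited events which stop vaccination are lost.* Protocol 3.1.4 includes the rule "The participant develops a Grade 3 systemic solicited adverse event considered possibly, probably or definitely related within 2 days after vaccination" (with persistence beyond 72 hours), while SAP 12.7.2.1 reads only the Unsolicited AEs page. But Protocol 8.2.4 also says "All adverse events, both those observed by study team members and those spontaneously reported by the participant, will be recorded in the eCRF", and the documents do not say on which page such an event goes. This is a separate clarification with no loss shown.

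**Conclusion.** The contradiction is certain: 8.2.4.3 cannot be reconciled as written with 5.2.1 or 3.1.4, and it sits badly with 8.2.1.1. Its effect is conditional. Where the sentence is followed, a count required by Protocol 10.2.2.6.1 is zero by construction, with the reach set out in step 3. Where sites record *Drug Withdrawn*, there is no loss from this sentence.

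The thing at risk is narrow: the flag that ties a particular AE to a stopped vaccine course. It does not extend to the event itself, its grade or relatedness, or the reason for a missed dose. The conclusion rests on reading the vaccine-only row as the vaccine limb of the SAP definition, and on the eCRF instructions being unknown. The documents give no discontinuation rate and none is assumed. The point should be fixed because it concerns a required safety tabulation and the remedy is small.

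**What to change.** - Reconcile 8.2.4.3 with 5.2.1, 3.1.4, 8.2.1.1 and the eCRF field, so that withdrawal of vaccine can be recorded against an event.
- Check the eCRF completion instructions for the same *None* rule.
- Before database lock, query AEs recorded as *None* in participants without dose 2 against the exposure and end-of-treatment reasons, and correct the field where an AE was the reason.
- As a secondary clarification, state whether a solicited event that stops vaccination is also entered on the Unsolicited AEs page that SAP 12.7.2.1 reads.

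The cost is one protocol sentence, one check of the instructions, a query limited to participants without dose 2, and one line of clarification. SAP version 2.0 is dated January 2023, and its change history already states that no participant had the Month 3 boost, which suggests that dosing was largely past. The data query is therefore the step most likely to change a result. A wider SAP rule that takes AEs from the reason a dose was not given is not proposed, because the documents do not show that this reason field identifies a specific AE. No dose or stopping rule is proposed.
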